6. HANDLING OF MISSING VALUES

For rwTR, patients who have inadequate data for tumor assessment (e.g. no baseline assessment or no post-baseline follow-up assessments), who receive anticancer medication other than the study medication prior to reaching a rwCR or rwPR, or who die, progress, or drop out for any reason prior to reaching a rwCR or rwPR will be counted as non-responders in the rwTR analysis.

No imputation for other missing values will be performed.

7. STATISTICAL METHODOLOGY AND STATISTICAL ANALYSES

7.1. Statistical methods

The inverse probability of treatment weighting (IPTW) technique will be used as the primary analysis method to control for confounders when comparing the cohorts. Propensity scores for use in IPTW will be calculated using a multivariable logistic regression model based on

PFIZER CONFIDENTIAL

the proposed baseline covariates in Section 5.2. Stabilized weights based on the propensity scores will be computed. The balance in important prognostic baseline characteristics will be assessed using a standardized differences approach, with values ≥ 0.10 indicating a non-negligible imbalance. After IPTW, no significant differences are expected among all pre-index measures between the patient cohorts, and the treatment effect that is calculated based on the weighted population is considered to be the true effect.

The Kaplan-Meier method adjusted by stabilized IPTW will be used to estimate median survival time and its 95% confidence intervals (CIs) for OS, rwPFS, and duration of treatment. Cox proportional models with a robust sandwich estimator adjusted by stabilized IPTW will be used to estimate hazard ratio and its 95% CIs for OS, rwPFS, and duration of treatment. The Cox model proportionality assumption will be evaluated by visually inspecting the Kaplan-Meier plot among the matched cohorts and confirmed by testing the significance of interactions between treatment modality and the log of time as well as each time-dependent covariate and the log of time. If the proportionality assumption is violated, an interaction term of time may be added.

OS and rwPFS rates at 12, 24, 36, 48, and 60 months will be estimated with corresponding 2-sided 95% CIs using the IPTW weighted Kaplan-Meier method.

Means, medians, and standard deviations will be provided for continuous variables when performing descriptive analysis of continuous data. Numbers and percentages will be provided for dichotomous and polychotomous variables when performing descriptive analysis of categorical data. Bivariate comparisons of baseline characteristics and outcomes measures will be provided. Appropriate tests (e.g., t-test, chi-square test) will be used based on the distribution of the measure. An unadjusted Kaplan Meier curve will be drawn to illustrate time-to-event.

All data analysis will be executed using statistical software SAS version 9.4 or later.

7.2. sensitivity analysis

1. PSM will be performed as a sensitivity analysis. Individual patients in the Palbociclib + Letrozole vs Letrozole alone cohorts will be matched by closest propensity scores. The Nearest Neighbor method (without replacement and with a caliper of 0.01) will be used to select the matched samples.
2. In Flatiron's definition of Line of Therapy, a 60-day time threshold is employed before advancing the line of therapy when CDK4/6i treatment is added to treatment with Aromatase Inhibitor (AI). A different time window will be adopted to advance the line of therapy, based on the distribution of the difference in the start time between AI and CDK4/6i as well as clinical judgment.

PFIZER CONFIDENTIAL

3. Depending on the pattern of missing tumor response assessments between the Palbociclib+AI and the AI alone arms, various methods will be explored to assess the impact of missing values on the tumor response result.

7.3. summary of Analyses

Outcome	Statistical Method
OS	Kaplan-Meier Plot, Cox proportional hazards model, IPTW/PSM
rwPFS	Kaplan-Meier Plot, Cox proportional hazards model, IPTW/PSM
Tumor response	Descriptive analyses and logistic regression analyses, IPTW/PSM
Time to treatment discontinuation	Kaplan-Meier Plot, Cox regression, summary of reason for discontinuation. Descriptive analysis and multivariate analyses to examine factors associated with time to discontinuation if sample size is large enough.
Time to next line of therapy	Kaplan-Meier Plot, Cox regression. Descriptive analysis and multivariate analyses to examine factors associated with time to next line of therapy if sample size is large enough.
Time to chemotherapy	Kaplan-Meier Plot, Cox regression. Descriptive analysis and multivariate analyses to examine factors associated with time to chemotherapy if sample size is large enough.
Initial dose of Palbociclib	Count of patients by initial dose level; summary of baseline and clinical characteristics by initial dose level; logistic regression of initial dose level on demographic and clinical characteristics; summary of rwTR by initial dose level; logistic regression of rwTR on initial dose level; KM estimates and Cox regression of rwPFS on initial dose level; KM estimates and Cox regression of time to treatment discontinuation on initial dose level; dose change from initial dose.
Dose adjustment	Describe dose changes of Palbociclib from initiation to discontinuation. Sankey diagram will be used as appropriate. Factors associated with dose adjustment will be examined by univariate and multivariate analyses as appropriate. Clinical outcomes (i.e, rwPFS, OS, and tumor response) associated with dose adjustment will be explored by Kaplan-Meier Plot, Cox regression, or logistic regression as appropriate.

PFIZER CONFIDENTIAL

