9. RESEARCH METHODS

9.1. Study design

The primary objective of the retrospective EHR database analysis is to compare effectiveness outcomes of palbociclib + AI versus AI alone as first line MBC treatment for HR+/HER2-MBC postmenopausal women or men.

The following table lists 7 key components of the study protocol.

D 4 10	D '.'
Protocol Component	Description
Eligibility criteria	All patients with HR+/HER2- MBC who were initiated with palbociclib + AI or AI alone as 1 st line therapy for their MBC during the period of February 2015 through March 2020 were registered in the Flatiron Health Analytic Database
Treatment regimen	Palbociclib + AI or AI alone as the first line MBC treatment
Study cohorts	Patients will be divided into either Palbociclib + AI or AI alone cohort according to their first line MBC treatment received
Follow-up period	From index date (i.e., starting date of the first line MBC treatment during the period of 03 February 2015 through March 2020) to death or study end (date of data cutoff, September 30, 2021), whichever occurred first
Primary outcome	Overall survival (OS)
Causal contrasts of interest	Intention-to-treat effect
Analysis plan	Intention-to-treat effect requires adjustments for baseline prognostic factors using IPTW approach. In addition, to address unmeasured confounding, sensitivity analyses will also be performed to determine the robustness of the estimated intention-to-treat effects.

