9.7.4.4. Sensitivity analyses

A concern with observational data is confounded by unmeasured or uncontrolled confounders; that is, could an unobserved factor related to both the treatment and outcome of interest explain an association, in the absence of a true causal effect. Sensitivity analyses are useful in assessing how robust an association is to potential unmeasured or uncontrolled confounding and are important tools to evaluating evidence for causation in the face of unmeasured confounding. Sensitivity analyses consider how strong unmeasured confounding would have to be to explain away the association, that is, how strongly the unmeasured confounder would have to be associated with the treatment and outcome for the treatment—outcome association not to be causal. Sensitivity analyses of missing data are also critical to evaluating the sensitivity of conclusions to violations in missing data assumptions. The following sensitivity analyses will be performed for the primary endpoint:

Propensity score matching (PSM) will be used as a sensitivity analysis to control
confounding. Propensity score matching creates sets of patients for treatment and
control cohorts. A matched set consists of at least 1 patient in the treatment group and
1 in the control group with similar propensity scores. The goal is to approximate a
random clinal trial, eliminating many of the problems that come with observational
data analysis. Matches will be made using 1:1 nearest neighbor matching without
replacement.

- Sensitivity analyses with the definition of the line of regimen by A1122 (i.e., the combination drugs were given within 28 days).
- Other sensitivity analyses may be conducted as needed, which will be described in the SAP.

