9.9. Limitations of the research methods

Given the retrospective nature of the study, some limitations are present including those typical of a data source where the primary purpose for collection was other than research. These include potential bias in treatment selection, incomplete or missing data, limited data on comorbidities, potential for inaccurate data capture, lack of scheduled assessments and lack of standardized assessment of tumor response or progression free survival. In addition, response to treatment and disease progression were determined based on the individual treating physician's clinical assessment or interpretation of radiographic scans or pathology results rather than a standard criterion such as RECIST.

Although IPTW will be used to balance patient characteristics and sensitivity analyses (e.g., PSM) will be conducted, other variables unavailable in the database, such as disease-free interval and prior therapy in neoadjuvant setting cannot be statistically controlled. Sample size may not be large enough for some subgroup analyses. Additionally, no causality could be made from the retrospective analysis. Moreover, these findings may not be generalizable to other patient populations.

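### The protocol promises a check of the OS result against unmeasured confounding, but no listed analysis provides one, and SAP 7.1 calls the weighted estimate the true effect, contrary to protocol 9.9

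*SAP*

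**What the plan says.** **The aim.** The analysis-plan row of the table in protocol 9.1 names an intention-to-treat causal contrast, adjusts for baseline prognostic factors by IPTW, and continues: "In addition, to address unmeasured confounding, sensitivity analyses will also be performed to determine the robustness of the estimated intention-to-treat effects". Protocol 9.7.4.4 opens with a general account of the problem and describes the kind of analysis meant: "Sensitivity analyses consider how strong unmeasured confounding would have to be to explain away the association". It then introduces a list of analyses to be done for the primary endpoint.

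**The list in protocol 9.7.4.4.**
- "Propensity score matching (PSM) will be used as a sensitivity analysis to control" confounding, with 1:1 nearest-neighbour matching without replacement.
- "Sensitivity analyses with the definition of the line of regimen by A1122", that is, a 28-day window for combination drugs.
- "Other sensitivity analyses may be conducted as needed, which will be described in the SAP".

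**The list in SAP 7.2.**
- "PSM will be performed as a sensitivity analysis", with a caliper of 0.01.
- A different time window for advancing the line of therapy.
- Unspecified methods for missing tumour-response assessments.

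**How the estimate is to be read.** SAP 7.1 checks balance with standardized differences (0.10 or more is non-negligible) and then says that "the treatment effect that is calculated based on the weighted population is considered to be the true effect". Protocol 9.9 says that, although IPTW and PSM will be used, variables not in the database cannot be controlled statistically, and that "no causality could be made from the retrospective analysis".

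**The concern.** Treatment was chosen by clinicians, not randomized, and protocol 9.9 itself lists bias in treatment selection as a limitation. The study nevertheless aims to demonstrate superiority on OS (9.7.1), and the protocol abstract reads a two-sided p below 0.05 as indicating an OS benefit. A reader of 9.1 and 9.7.4.4 will expect an analysis showing how much hidden confounding that result could withstand. Neither document names one: there is no E-value, bias-factor array, negative control, instrument or tipping-point analysis for OS. Protocol 9.7.4.4 leaves further analyses to the SAP, and the SAP adds none for this purpose.

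The SAP sentence makes matters worse. A balance check can only cover recorded variables, so passing it does not entitle the weighted estimate to be called the true effect.

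**Working it through.** **1. Can any listed analysis do what is promised for OS?**
- *PSM.* The SAP gives one covariate list for the propensity score (5.2). Matching and weighting both use the score built from measured variables, so a factor absent from the score can bias both in the same direction. Their agreement carries no information about that factor.
- *Line-of-therapy window.* This changes who counts as palbociclib + AI. It tests exposure classification.
- *Missing tumour response.* This concerns rwTR, not OS.

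One related inconsistency: protocol 9.9 gives disease-free interval as an example of a variable that is unavailable, while protocol 9.7.4.1 and SAP 5.2 list it as a propensity score covariate. Which confounders are unmeasured is therefore itself unclear.

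**2. The plan's own design figure (protocol 9.7.2).** The inputs are HR 0.80, two-sided alpha 0.05, about 1:1 allocation and 750 deaths. Schoenfeld events for 80% power: 4 × (1.960 + 0.842)² / (ln 0.80)² = 631. With 750 deaths power is 86.3%, so the stated minimum of 80% is met. The surplus is conservative and has no bearing on this point.

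**3. Precision at 750 deaths (unweighted approximation).** SE of ln HR = 2/√750 = 0.0730.
- Largest significant HR: exp(−1.96 × 0.0730) = 0.867.
- Upper 95% limit at an observed HR of 0.80: 0.80 × exp(1.96 × 0.0730) = 0.923.

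**4. E-values.** Death is a common outcome here, so convert first: RR = (1 − 0.5^√HR) / (1 − 0.5^√(1/HR)). Then E = 1/RR + √[(1/RR)(1/RR − 1)]. E is the minimum association, on the risk-ratio scale, that a hidden factor would need with both treatment and death to move the estimate to 1.

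| HR | Source | RR | E-value |
|---|---|---|---|
| 0.80 | design value, protocol 9.7.2 | 0.857 | 1.61 |
| 0.923 | upper limit at 0.80, step 3 | 0.946 | 1.30 |
| 0.867 | just significant, step 3 | 0.906 | 1.44 |
| 0.66 | previous Flatiron study of palbociclib + letrozole, protocol abstract | 0.750 | 2.00 |
| 0.82 | upper limit of that study | 0.872 | 1.56 |

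Without the conversion the first two E-values would be 1.81 and 1.38.

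**5. A worked bias factor (assumed inputs).** Take a binary factor that doubles the hazard, present in 15% of palbociclib + AI patients and 30% of AI-alone patients, with no drug effect. The approximate spurious HR is (1 + 0.15)/(1 + 0.30) = 0.885. On the log scale that is ln 0.885 / ln 0.80 = 0.55 of the design effect. Against the SE in step 3, z = 0.1226/0.0730 = 1.68, so the expected result is not significant. The chance of a significant benefit is Φ(1.68 − 1.96), about 39%.

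Other assumed inputs move this widely. With the hazard still doubled, prevalences of 30% v 40% give HR 0.929 and a 17% chance; 20% v 40% give 0.857 and 56%.

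**6. Does matching reveal the bias?** A simulation used N = 3000, about 766 deaths, no drug effect, and one omitted factor independent of the measured covariates (HR 2.0, prevalence 26% v 44%; all assumed), over 200 runs. The mean HR was 0.869 by stabilized IPTW and 0.866 by PSM with the 0.01 caliper. Weighted standardized differences for the measured covariates stayed below 0.02, so the 0.10 check passed in every run. Matching reproduced the bias.

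**The case against.** The best answer is protocol 9.9. It says that, even with IPTW and PSM, variables missing from the database cannot be controlled, and it rules out causal conclusions. That stands, and it limits what can be claimed here. A reader might infer that the study would declare its OS result robust to unmeasured confounding once IPTW and PSM agree, so that a confounded benefit would pass unchallenged. The documents do not support that: neither contains such a rule or such report wording, and 9.9 points the other way. Nor do they rank unmeasured confounding as the main threat. Protocol 9.7.4.4 calls it a concern, and 9.8 calls missing death data a major confounding factor in such analyses.

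Other points also stand in part:
- The true-effect sentence changes no estimator, test or threshold. It is wording, but wording in the document that governs the analysis.
- An E-value can be computed by anyone from a published HR and interval, and the omission does not itself bias the estimate.
- The study is intended for publication only (protocol section 5) and is not a regulatory commitment (section 7).
- The explain-away language is in the general introduction to 9.7.4.4, and PSM's stated purpose there is simply to control confounding. But 9.1 attaches the unmeasured-confounding aim to this study's own analysis plan.
- Protocol 9.7.4.4 allows further analyses, and the SAP describes itself as a first draft. That leaves room to close the gap but does not close it.

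**Conclusion.** The point holds in a limited form. The protocol states an aim, to examine how far unmeasured confounding could account for the OS association, that no listed analysis can meet. SAP 7.1 contradicts protocol 9.9 on how the weighted estimate is to be read. Residual confounding is acknowledged, but only in narrative.

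The E-values (1.61 at HR 0.80, 1.30 at its upper limit) suggest that fairly modest hidden confounding could remove significance at the design effect. They rest on 750 deaths, 1:1 allocation, an unweighted standard error and the common-outcome conversion. The prevalences and hazard ratios in the bias examples are assumptions and appear in neither document. They show that the bias could matter, not that it is present, and the 15% v 30% example does not reach significance in expectation. This should be fixed, but it does not invalidate the primary analysis.

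**What to change.** 1. In SAP 7.1, replace the true-effect wording with *covariate-adjusted estimate, subject to unmeasured confounding*, in line with protocol 9.9.
2. In protocol 9.7.4.4 and SAP 7.2, pre-specify at least one quantitative bias analysis for OS. One suitable choice is the E-value for the stabilized-IPTW hazard ratio and for the confidence limit nearest 1, with the conversion formula stated. A bias-factor grid is optional. If used, its prevalence and hazard ranges should be justified and labelled as assumptions.
3. In SAP 7.2, carry over the caveat in 9.9 by stating that PSM addresses measured confounding only.

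While editing, reconcile whether disease-free interval is available. Protocol section 6 planned the primary analyses to start on 01 September 2021; if OS has already been analysed, the addition should be labelled as made afterwards.

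The cost is a few sentences and a closed-form calculation, with no new data. The conclusion may read less favourably.

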be used to compute a propensity-to-treatment score (PS) by a logistic regression model, where the outcome variable is being in the palbociclib + AI group (yes, no). The individual PS is used to obtain the individual IPTW which is applied to the observations to assess the balance between treatment arms in the potential confounders after weighting.

If the method of IPTW yields balanced treatment groups with respect to the potentially measured confounders, then a weighted log-rank test using IPTW will be used to compare OS between the palbociclib + AI group and the AI alone group, with a nominal p< 0.05, two-sided, indicating an OS benefit in the palbociclib + AI group. The weighted Cox proportional hazards model will be used to compute the hazard ratio and the corresponding 95% CI. If the method of IPTW does not yield balanced treatment groups with respect to the potential confounders, analysis by PS quintiles will be used. All subjects will be stratified in quintiles based on the PS. A stratified log-rank test (stratified by PS quintiles) will be used to compare OS between the palbociclib + AI group and the AI alone group, with a nominal p< 0.05, two-sided, indicating an OS benefit in the palbociclib + AI group. This method allows for the comparison of subjects with similar PS without the potential loss of subjects in 1-1 matching. A stratified Cox proportional hazards model (stratified by PS quintiles) will be used to compute the hazard ratio and the corresponding 95%CI.

These time-to-event endpoints will also be summarized using the weighted Kaplan-Meier method and displayed graphically where appropriate. Similar analyses will be performed for rwPFS. Logistic regression analysis will be performed to compare rwTR between the 2 treatment groups. Descriptive analyses will be performed to report baseline patient demographics and clinical characteristics, treatment patterns, and time to next line of systemic anticancer therapy from palbociclib + AI initiation. Subgroup analyses will be conducted according to age, ethnicity, ECOG performance, metastatic site (i.e. visceral, bone only, etc.), and endocrine sensitivity as sample sizes allow.

A detailed statistical analysis plan (SAP) will be developed separately.

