9.7.2. Sample size determination

Approximately 3000 patients will be included with close to a 1:1 ratio between palbociclib + AI and AI alone cohorts. The median OS for AI alone is assumed to be 40 months. An improvement of 25% to a median OS of 50 months (corresponding to a hazard ratio of 0.80) would be considered clinically meaningful. Therefore, 750 OS events will be required to have at least 80% power to detect a hazard ratio of 0.80 using a two-sided log-rank test at a significance level of 0.05 based on the exponential distribution assumptions of OS for both cohorts.

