3.2. Statistical decision rules

The alpha level will be 0.05, 2-sided. No adjustments for multiple comparisons will be made.

3.3. sample size calculation

Approximately 3000 patients will be included with close to a 1:1 ratio between palbociclib + AI and AI alone cohorts. **CCI**

PFIZER CONFIDENTIAL

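### The IPTW hazard-ratio intervals use a sandwich variance that makes no stated allowance for estimating the propensity score, so they tend to be somewhat too wide

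*SAP*

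**What the plan says.** SAP 7.1 states that propensity scores will be "calculated using a multivariable logistic regression model based on" the baseline covariates of SAP 5.2. Those are age, race, practice type, ECOG score, stage at initial diagnosis, visceral metastasis, number of disease sites, disease-free interval and comorbidities. It continues: "Stabilized weights based on the propensity scores will be computed". For the hazard ratios of OS, rwPFS and duration of treatment it says "Cox proportional models with a robust sandwich estimator adjusted by stabilized IPTW will be used to estimate hazard ratio and its 95% CIs". No bootstrap, and no variance that includes the propensity model, is named in either document.

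The protocol's primary comparison is a test. Provided weighting achieves balance, the Abstract says "then a weighted log-rank test using IPTW will be used to compare OS" between the two groups. Protocol 9.7.4.2 repeats the weighted log-rank test, calling it one-sided while setting a two-sided 0.05 level in the same sentence. Neither place gives a variance for the weighted test. SAP 7.1 and the SAP 7.3 summary table name Kaplan-Meier and Cox methods for OS but no log-rank test. SAP 3.2 says "The alpha level will be 0.05, 2-sided. No adjustments for multiple comparisons will be made".

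On study size, Protocol 9.7.2 says "Approximately 3000 patients will be included with close to a 1:1 ratio between palbociclib + AI and AI alone cohorts". It plans with a control-cohort median of 40 months, and on power it says "750 OS events will be required to have at least 80% power to detect a hazard ratio of 0.80 using a two-sided log-rank test".

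**The concern.** The weights are functions of coefficients fitted to the same patients. A weighted Cox sandwich that takes the weights as fixed leaves out the part of the estimator's behaviour that comes from fitting those coefficients. In inverse probability weighting that omission normally overstates the variance, because fitting the propensity model removes some chance imbalance in the covariates. The more prognostic the covariates, the more is removed and the larger the overstatement. Several SAP 5.2 covariates (ECOG, stage, visceral disease, number of sites) are of a kind one would expect to be prognostic, and SAP 7.1 itself speaks of balancing prognostic characteristics.

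The stake is precision: an interval wider than the data warrant, and some loss of power if the decision follows that interval. A second stake is consistency. The protocol decides on a log-rank p-value, while the SAP reports a Cox interval. With no variance stated for the first, the programmer chooses whether the two rest on the same error calculation.

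**Working it through.** **1. The plan's own figure.** Schoenfeld, 1:1, two-sided 0.05, HR 0.80:

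events = 4(1.960 + 0.842)² / (ln 0.80)² = 31.40 / 0.0498 = 631 for 80% power (Freedman: 636).

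At 750 events, SE = 2/√750 = 0.0730, z = 0.2231/0.0730 = 3.056, and power = Φ(3.056 − 1.960) = 86.3%. So 750 is not the minimum for 80%, but the claim of at least 80% power is true. It serves below only as a scale.

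**2. Direction.** Let ψᵢ be patient i's contribution to the weighted Cox score and I the weighted information. With weights taken as known,

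SE_fixed = √(Σψᵢ²) / I.

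With a correctly specified logistic model, allowing for its estimation replaces ψᵢ by its residual after least-squares projection on the logistic score Sᵢ = Xᵢ(Aᵢ − êᵢ):

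SE_adj = √(Σ(ψᵢ − Sᵢγ)²) / I.

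A residual sum of squares cannot exceed the total, so SE_adj ≤ SE_fixed. The gap depends on how much of ψ the covariates explain.

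**3. Size.** Inputs from the documents: 3000 patients, about 1:1, control median 40 months, HR 0.80, nine covariates, logistic propensity score, stabilized weights without truncation. Assumed: independent standard normal covariates, their strengths, and censoring set to give about 710-880 deaths. There were 4000 replicates per scenario. Entries are log coefficients per SD, for each covariate.

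| Prognosis / selection | Deaths | Empirical SE | SE_fixed / empirical | SE_adj / empirical | Coverage, SE_fixed |
|---|---|---|---|---|---|
| weak 0.05 / 0.25 | 710 | 0.0825 | 0.99 | 0.99 | 94.6% |
| weak 0.05 / 0.45 | 712 | 0.1014 | 0.98 | 0.98 | 95.0% |
| moderate 0.20 / 0.25 | 777 | 0.0771 | 1.04 | 0.98 | 95.8% |
| strong 0.35 / 0.25 | 879 | 0.0671 | 1.13 | 0.98 | 97.7% |
| strong 0.35 / 0.45 | 884 | 0.0872 | 1.12 | 0.97 | 97.6% |

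Coverage is measured around the mean estimate. Monte Carlo error is about 1.1% on an SE ratio (1/√(2 × 3999)) and about 0.3 points on coverage, so the two weak rows cannot be told apart from no excess. The moderate setting with HR 0.86 also gave 1.04.

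A separate simulation with nine mixed continuous and binary covariates and about 835-955 deaths gave ratios of 1.01, 1.05, 1.06 and 1.10 from weakly to strongly prognostic, against 0.97-1.01 for the propensity-adjusted variance.

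**4. What a ratio r means.** As an illustration, suppose the true SE equals the planning value 0.0730. Then power = Φ(3.056 − 1.960r), two-sided error = 2[1 − Φ(1.960r)], and the equivalent share of deaths lost = 1 − 1/r².

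| r | Power | Two-sided error | Deaths lost |
|---|---|---|---|
| 1.00 | 86.3% | 5.0% | 0% |
| 1.04 | 84.5% | 4.2% | 8% |
| 1.06 | 83.6% | 3.8% | 11% |
| 1.10 | 81.6% | 3.1% | 17% |
| 1.13 | 80.0% | 2.7% | 22% |

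**5. Log-rank against Cox interval.** Across the scenarios in step 3, including the HR 0.86 one, the share of datasets with different 5% verdicts was:
- 0.3%-3.4% if the weighted log-rank uses a robust variance;
- 0.9%-7.3% with a null variance that takes the weights as known;
- 4.3%-24.2% with a naive variance that treats the weights as case counts.

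The documents do not say which would be used.

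**The case against.** The strongest reply is that a slightly conservative, pre-specified variance is a defensible choice in an observational study. Protocol 9.7.1 says that about 75% of the deaths come from an earlier study in which an OS benefit had already been seen. The alternative is not free of error either: the propensity-adjusted SE was 0.97-0.99 of the empirical SE in the simulation tabulated above, so very slightly small. Both points stand. They limit the severity, but they do not make the ordinary sandwich the better estimate of the variance.

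A reader might infer more than the documents support in four ways.

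- **That the interval is certainly too wide.** The documents give no association of any covariate with treatment or survival. SAP 5.2 bases the list on clinical judgment, and it includes race and practice type, whose prognostic strength is equally unstated. With weak covariates the excess was nil.
- **That the loss is larger.** A simulation with six covariates and about 1,360-1,400 deaths gave an excess of 5%-17%. That is nearly twice the planned 750 deaths, and neither end of the range was reproduced near the planned count.
- **That the interval fails, or type I error is inflated.** Coverage was 94.6%-97.7%. Departures beyond Monte Carlo error were all on the conservative side.
- **That the p-value and the interval disagree.** This is possible, not shown. Frequent disagreement needs a naive log-rank variance, which neither document specifies; with a matching robust variance it was at most 3.4%.

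**Conclusion.** The point holds as a tendency. As written, SAP 7.1 makes no allowance for estimating the propensity score, and the usual sandwich then overstates the standard error by about nothing with weakly prognostic covariates, about 4-6% with moderate ones and about 10-13% with strong ones. These figures rest on assumed covariate strengths and on event counts of roughly 710-955. The documents cannot place this study within the range. The calculations used a single survival outcome; the same reasoning applies to rwPFS and duration of treatment, but no size was computed for them.

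The consequence is lost precision and conservative coverage, not a false claim of superiority. The gap between the protocol's log-rank test and the SAP's Cox analysis is one of specification: the test has no variance, is absent from the SAP, and is described as both one-sided and two-sided in Protocol 9.7.4.2. Protocol 9.7 says that major changes to the primary analysis will also be reflected in a protocol amendment, yet the current protocol still carries the test. Severity is minor: a cheap improvement.

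**What to change.** In SAP 7.1, take the 95% CI and p-value for the weighted OS and rwPFS hazard ratios from one of two sources:

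- a nonparametric bootstrap that resamples patients and refits the propensity model and stabilized weights in every resample, with the number of resamples (for example 1,000) and the seed fixed in advance; or
- a sandwich that includes the propensity-score estimating equations.

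Base the primary OS decision on that same variance. If the weighted log-rank test is kept, name it in the SAP, give it a variance consistent with the interval, and make its sidedness agree between Protocol 9.7.4.2 and SAP 3.2. Report the ordinary sandwich interval as a check.

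The cost is a few lines of SAP text (and matching protocol wording), computing time, a pre-specified seed if the bootstrap is used, and an interval somewhat less conservative than the present one. No new data are needed.
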